5.4.3 Physical Examinations

The analyses of physical examinations will include summary statistics (actual value and change from Baseline for body weight and height) over time by visit.

5.4.4 Vital Signs

The analysis of vital signs will focus on clinically relevant abnormalities. For each vital sign, the number of subjects evaluated and the number and percentage of subjects with the defined abnormality at any time post-baseline will be presented.

The definitions of these clinically relevant abnormalities are shown in [Table 4](#).

Table 4: Criteria to Determine Clinically Relevant Abnormalities in Vital Signs

Vital Sign	Criteria for Abnormalities
Temperature	>38°C post baseline and an increase from Baseline of $\geq 1^{\circ}\text{C}$
Pulse	>120 bpm post baseline or an increase from Baseline of >20 bpm <50 post baseline bpm or a decrease from Baseline of >20 bpm
Systolic Blood Pressure	>180 mmHg post baseline or an increase from Baseline of >40 mmHg <90 mmHg post baseline or a decrease from Baseline of >30 mmHg
Diastolic Blood Pressure	>105 mmHg post baseline or an increase from Baseline of >30 mmHg <50 mmHg post baseline or a decrease from Baseline of >20 mmHg

The analyses of vital signs will also include summary statistics (actual value and change from Baseline for temperature, pulse, and systolic and diastolic blood pressure) over time by visit.

CONFIDENTIAL

The information contained herein may not be used, disclosed, or published without the written consent of Biogen Idec MA Inc.

	Protocol 109MS310 An Open-Label Study to Assess the Effects of BG00012 on Lymphocyte Subsets in Subjects With RRMS	Final Version 1.0
---	---	--------------------------

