16.4.2.4. Vital Signs

The analysis of vital signs will focus on clinically relevant abnormalities. The number of subjects evaluated and the number and percentage of subjects with clinically relevant post-Baseline abnormalities will be presented by group.

The definitions of these clinically relevant abnormalities are shown in [Table 5](#).

Table 5: Criteria to Determine Clinically Relevant Abnormalities in Vital Signs

Vital Sign	Criteria for Abnormalities
Temperature	>38°C or an increase from Baseline of $\geq 1^{\circ}\text{C}$
Pulse	>120 bpm or an increase from Baseline of >20 bpm <50 bpm or a decrease from Baseline of >20 bpm
Systolic Blood Pressure	>180 mmHg or an increase from Baseline of >40 mmHg <90 mmHg or a decrease from Baseline of >30 mmHg
Diastolic Blood Pressure	>105 mmHg or an increase from Baseline of >30 mmHg <50 mmHg or a decrease from Baseline of >20 mmHg

The analyses of vital signs will also include summary statistics (actual value and change from Baseline for temperature, pulse, and systolic and diastolic blood pressure) over time by visit.

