5.7 Changes in statistical analysis methods

5.7.1 Change in clinical assessment population definition

In protocol, the evaluable population for clinical assessments is defined as all subjects who receive at least 1 dose of study treatment and at least 1 measurement for each of the clinical assessments after Baseline. [REDACTED]

[REDACTED]

[REDACTED]

CONFIDENTIAL

The information contained herein may not be used, disclosed, or published without the written consent of
Biogen Idec MA Inc.

biogen idec	Protocol 109MS310 An Open-Label Study to Assess the Effects of BG00012 on Lymphocyte Subsets in Subjects With RRMS	Final Version 1.0
--------------------	---	--------------------------

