Appendix 2 – Visit windowing rules

For Blood Chemistry, window to scheduled visits using the following windows:

Visit Name	Target Day	Study Day in Range Window
Baseline	first dose date	<= first dose date
Week 4	Day 29	(first dose date+1) to Day 42
Week 8	Day 57	Day 43 to Day 112
Week 24	Day 169	Day 113 to Day 252
Week 48	Day 337	Day 253 to Day 504
Week 96	Day 673	>=Day 505

For Hematology parameters, window to scheduled visits using the following windows:

Visit Name	Target Day	Study Day in Range Window
Baseline	first dose date	<= first dose date
Week 4	Day 29	(first dose date+1) to Day 42
Week 8	Day 57	Day 43 to Day 70
Week 12	Day 85	Day 71 to Day 126
Week 24	Day 169	Day 127 to Day 210
Week 36	Day 253	Day 211 to Day 294
Week 48	Day 337	Day 295 to Day 378
Week 60	Day 421	Day 379 to Day 462
Week 72	Day 505	Day 463 to Day 546
Week 84	Day 589	Day 547 to Day 630
Week 96	Day 673	>=Day 631

CONFIDENTIAL

The information contained herein may not be used, disclosed, or published without the written consent of Biogen Idec MA Inc.

biogen idec	Protocol 109MS310 An Open-Label Study to Assess the Effects of BG00012 on Lymphocyte Subsets in Subjects With RRMS	Final Version 1.0
--------------------	---	--------------------------

For the lymphocyte subsets, IgS and vital signs, window to scheduled visits using the following windows:

Visit Name	Target Day	Study Day in Range Window
Baseline	first dose date	<= first dose date
Week 4	Day 29	(first dose date+1) to Day 42
Week 8	Day 57	Day 43 to Day 70
Week 12	Day 85	Day 71 to Day 126
Week 24	Day 169	Day 127 to Day 210
Week 36	Day 253	Day 211 to Day 294
Week 48	Day 337	Day 295 to Day 420
Week 72	Day 505	Day 421 to Day 588
Week 96	Day 673	>=Day 589

For the physical exam (weight and height), window to scheduled visits using the following windows:

[figure not shown]
Visit Name	Target Day	Study Day in Range Window
Baseline	first dose date	<= first dose date
Week 48	Day 337	(first dose date+1) to Day 504
Week 96	Day 673	>=Day 505

CONFIDENTIAL

The information contained herein may not be used, disclosed, or published without the written consent of Biogen Idec MA Inc.

For the lymphocyte subsets in the lymphocyte follow-up period, window to scheduled visits using the following windows:

Visit Name	Target Day	Study Day in Range Window
Lymphocyte FU Baseline	lymphocyte follow-up start date	<= lymphocyte follow-up start date
4 weeks from Lymphocyte FU baseline	Day 29	Day 2 to Day 42

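### The SAP requires both >38°C and a rise of at least 1°C for a temperature abnormality where the protocol requires either, so some protocol-defined events, possibly many, will not be counted

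*SAP*

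**What the plan says.** **Protocol 16.4.2.4, Table 5.** A temperature is abnormal if it is ">38°C or an increase from Baseline of" at least 1°C. The output is a subject count: "the number and percentage of subjects with clinically relevant post-Baseline abnormalities will be presented by group". Version 1 of the protocol, reproduced in the same file, has the same 'or'.

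**SAP 5.4.4, vital-signs criteria table.** (The SAP has two tables numbered 4. This is the second.) A temperature is abnormal if it is ">38°C post baseline and an increase from Baseline of" at least 1°C. The other rows keep the protocol's connective; pulse, for example, reads ">120 bpm post baseline or an increase from Baseline of >20 bpm". The output is again a subject count: "the number and percentage of subjects with the defined abnormality at any time post-baseline will be presented".

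**SAP 5.7.** This section is for departures from the protocol's methods. Its only visible entry is 5.7.1, "Change in clinical assessment population definition". Text below that heading is redacted. The SAP contents list also shows only 5.7.1 under 5.7.

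**The concern.** The two documents give different rules for the same safety output, and only the temperature row differs. The SAP table carries the protocol table's title and thresholds, so nothing tells a reader that one row now means something else.

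The change runs in one direction, towards fewer flagged subjects. In a study of a drug known to lower lymphocyte counts, an objective temperature reading complements the reported infections. Narrowing that criterion should be a stated decision. The documents do not show whether 'and' was a slip or a choice.

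**Working it through.** Neither document states an expected number of temperature abnormalities, so there is no plan figure to reproduce. The check is one of logic, followed by an illustration of size on stated assumptions.

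**Step 1: direction.** Let B be the baseline temperature and T a post-baseline reading. The protocol set is {T > 38 or T − B ≥ 1}. The SAP set is {T > 38 and T − B ≥ 1}. The second lies inside the first for every reading, and therefore for every subject counted at any time post-baseline. So SAP count ≤ protocol count, always.

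**Step 2: which readings drop out.** The dividing line is a baseline of 37.0°C.

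- If B ≤ 37.0, any T > 38 is already a rise of more than 1°C. The protocol rule reduces to a rise of at least 1°C, and the SAP rule to T > 38. Rises of at least 1°C that end at or below 38°C are lost. Example: 36.2 to 37.3°C, a rise of 37.3 − 36.2 = 1.1°C.
- If B > 37.0, any rise of at least 1°C already exceeds 38°C. The protocol rule reduces to T > 38, and the SAP rule to the rise. Readings above 38°C with a rise below 1°C are lost. Example: 37.2 to 38.1°C, a rise of 38.1 − 37.2 = 0.9°C.

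**Step 3: size, by assumption.** From the documents: vital signs are taken after Baseline at Weeks 4, 8, 12, 24, 36, 48, 72 and 96 and at the final Follow-Up Visit, giving 9 readings; 200 subjects are planned. Assumed, because the documents are silent: mean 36.4 to 36.8°C, between-subject SD 0.2 to 0.3, within-subject SD 0.2 to 0.4, and fever of 38.1 to 39.5°C at 0 to 2% of post-baseline visits. Readings are normal and rounded to 0.1°C, with 200,000 simulated subjects per scenario. Share lost = 1 − (SAP count / protocol count).

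| Mean; between-SD | Within-SD | Fever visits | Protocol 'or', per 200 | SAP 'and', per 200 | Share lost |
|---|---|---|---|---|---|
| 36.4; 0.2 | 0.2 | 2% | 33.7 | 33.1 | 2% |
| 36.6; 0.3 | 0.2 | 0.5% | 9.6 | 8.9 | 8% |
| 36.6; 0.3 | 0.3 | 2% | 46.4 | 33.1 | 29% |
| 36.6; 0.3 | 0.3 | 0.5% | 23.7 | 8.8 | 63% |
| 36.6; 0.3 | 0.4 | 0.5% | 52.5 | 10.4 | 80% |
| 36.4; 0.2 | 0.3 | 0 | 15.4 | 0.0 | 100% |

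The loss is a minority when most flagged subjects have true fevers. It is a majority when ordinary variation produces most of the 1°C rises.

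**Step 4: true fevers.** A fever F is lost under 'and' only if B > F − 1. Take F uniform on 38.1 to 39.5°C and B normal with mean 36.6 and SD s (assumed). The lost share is the average upper-tail probability of z from (37.1 − 36.6)/s to (38.5 − 36.6)/s, approximately [φ(a) − a(1 − Φ(a))] / (b − a), where a and b are those two limits.

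- s = 0.5: a = 1.0, b = 3.8; (0.2420 − 0.1587)/2.8 = 0.030, so about 97% of fevers are kept.
- s = 0.3: a = 1.667, b = 6.333; (0.0995 − 1.667 × 0.0478)/4.667 = 0.004, so about 99.6% are kept.

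**The case against.** The strongest reply is that the omission is mostly harmless. A reading above 38°C is lost only when baseline was already above 37.0°C, and step 4 suggests that 'and' keeps nearly all true fevers. What 'or' adds is largely afebrile variation. With no true fevers at all, mean 36.6°C, total SD 0.3 to 0.5 and within-subject correlation 0.3 to 0.5, 'or' still flags roughly 0.4% to 23% of subjects, and 87% to over 99% of those never exceed 38°C. On that view 'and' may be a deliberate gain in specificity. This stands as a reason not to assume that 'or' is the better rule. It does not excuse an unexplained difference between the documents.

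It is also fair to say that other outputs cover much of the ground. SAP 5.4.1 tabulates infections, serious infections and potential opportunistic infections by ALC subgroup and lists any PML case. SAP 5.4.4 summarises "change from Baseline for temperature, pulse, and systolic and diastolic blood pressure) over time by visit", and continuous summaries include the minimum and maximum, so extreme values remain visible. Temperatures at visits 4 to 24 weeks apart are in any case a weak detector of infection. All of this limits the impact. None of it gives the number of subjects meeting the protocol's criterion, and SAP 5.4.4 promises no vital-sign listing from which to recover it.

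A reader might infer that most protocol-defined events will go uncounted. The documents do not support that. They give no temperature distribution or fever rate, and simulations without fevers build a large gap in from the start.

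**Conclusion.** Wrong as written, with limited impact. The mismatch and its direction are certain from the text: the SAP count can only equal or fall below the protocol count. That the change is undeclared rests on the visible text of SAP 5.7 and its contents entry, so it is likely rather than proven, given the redaction.

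The size is not determined by the documents. The range of about 2% to 100% of protocol-positive subjects depends wholly on the assumed temperature variation and fever rate; the supportable statement is 'some, possibly many'. A reader might also infer that the SAP table would miss infection-related fevers. On the assumptions shown, most would still be counted.

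The affected output is one descriptive table in a single-arm study. No primary or secondary endpoint is touched.

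**What to change.** Reconcile the two definitions. Either put the protocol's 'or' in the temperature row of the SAP 5.4.4 table, or, if 'and' is intended, declare it in SAP 5.7 with the reason.

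In either case report three temperature counts: subjects with any reading above 38°C, subjects with any rise of at least 1°C, and subjects with both at the same reading. The reader can then see how much depends on the connective. Cite the table by title, because its number is duplicated.

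The cost is one word or one short entry in SAP 5.7, plus one or two table rows. No new data are needed.

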5.4.5 ECG Data

A listing of subjects with abnormal ECG status will be presented. The number and percentage of subjects with shifts from baseline to each of the categorical values denoting an abnormal scan (abnormal, not AE/abnormal, AE) will be summarized.

5.4.6 Safety analysis during lymphocyte follow-up period

[figure not shown]
The concomitant medication, AEs, hematology, vital signs and physical examination data collected during the lymphocyte follow-up period will be analyzed.

The concomitant medication and AEs, either started prior to the lymphocyte follow-up period and continued during the lymphocyte follow-up period, or started on or after the lymphocyte follow-up period will be listed.

Hematology, vital signs and physical examination data during the lymphocyte follow-up period will either be descriptively summarized or listed. The windowing rule defined in [Section 5.3.3](#) will be used for visit mapping. Additional safety analyses during lymphocyte follow-up period may be conducted.

[figure not shown]
CONFIDENTIAL

The information contained herein may not be used, disclosed, or published without the written consent of Biogen Idec MA Inc.

CONFIDENTIAL

The information contained herein may not be used, disclosed, or published without the written consent of
Biogen Idec MA Inc.

5.7 Changes in statistical analysis methods

5.7.1 Change in clinical assessment population definition

In protocol, the evaluable population for clinical assessments is defined as all subjects who receive at least 1 dose of study treatment and at least 1 measurement for each of the clinical assessments after Baseline. [REDACTED]

[REDACTED]

[REDACTED]

CONFIDENTIAL

The information contained herein may not be used, disclosed, or published without the written consent of
Biogen Idec MA Inc.

biogen idec	Protocol 109MS310 An Open-Label Study to Assess the Effects of BG00012 on Lymphocyte Subsets in Subjects With RRMS	Final Version 1.0
--------------------	---	--------------------------

Appendix 1 – List of reportable lymphocyte subset parameters

Lab test name (LabCorp)	Lab test code (LabCorp)	Lab label	Subset type
%CD24hi/CD38hi [CD19+/CD3-]	BCSB03	Transitional B-cells (% of B cells)	B Cell Subsets
%CD24hi/CD38hi/CD10+ [19+/3-]	BCSB08	CD10+ Transitional B cells (% of B cells)	B Cell Subsets
%CD27++/CD38++ [CD19+/CD3-]	BCSB09	Plasmablasts (% of B cells)	B Cell Subsets
%CD27++/CD38++/CD10- [19+/3-]	BCSB10	Plasma Cells [CD10-] (% of B cells)	B Cell Subsets
%CD27++/CD38++/CD138+ [19+/3-]	BCSB12	CD138+ Plasma Cells (% of B cells)	B Cell Subsets
%CD27+/IgD+ [CD19+/CD3-]	BCSB07	IgD+ Memory B cells [non-class switched] (% of B cells)	B Cell Subsets
%CD27+/IgD- [CD19+/CD3-]	BCSB06	IgD- Memory B cells [class switched] (% of B cells)	B Cell Subsets
%CD27-/IgD+ [CD19+/CD3-]	BCSB05	Naïve B cells (% of B cells)	B Cell Subsets
Absolute 27++/38++/10-[19+/3-]	BCSB22	Plasma Cells [CD10-] (cells/mm3)	B Cell Subsets
Absolute CD24hi/CD38hi[19+/3-]	BCSB15	Transitional B-cells (cells/mm3)	B Cell Subsets
Absolute CD27++/38++[19+/3-]	BCSB21	Plasmablasts (cells/mm3)	B Cell Subsets
Absolute CD27+/IgD+ [CD19+/3-]	BCSB19	IgD+ Memory B cells [non-class switched] (cells/mm3)	B Cell Subsets
Absolute CD27+/IgD- [CD19+/3-]	BCSB18	IgD- Memory B cells [class switched] (cells/mm3)	B Cell Subsets
Absolute CD27-/IgD+ [CD19+/3-]	BCSB17	Naïve B cells (cells/mm3)	B Cell Subsets
Absolute24hi/38hi/10+[19+/3-]	BCSB20	CD10+ Transitional B cells (cells/mm3)	B Cell Subsets
Absolute27++/38++/138+[19+MNC]	BCSB24	CD138+ Plasma Cells (cells/mm3)	B Cell Subsets
%CD11a+ [CD11c++]	A4S96	CD11a+ (% of dendritic cells [CD11c++])	VLA-4/LFA-1 Expression
%CD11a+ [CD19+]	A4S82	CD11a+ (% of B cells)	VLA-4/LFA-1 Expression
%CD11a+ [CD3+]	A4S68	CD11a+ (% of T cells)	VLA-4/LFA-1 Expression
%CD11a+ [Lymphs]	A4S26	CD11a+ (% of lymphocytes)	VLA-4/LFA-1 Expression
%CD11a+ [MNC]	A4S12	CD11a+ (% of MNC)	VLA-4/LFA-1 Expression
%CD11a+ [Monos]	A4S40	CD11a+ (% of monocytes)	VLA-4/LFA-1 Expression

CONFIDENTIAL

The information contained herein may not be used, disclosed, or published without the written consent of Biogen Idec MA Inc.

biogen idec	Protocol 109MS310 An Open-Label Study to Assess the Effects of BG00012 on Lymphocyte Subsets in Subjects With RRMS	Final Version 1.0
--------------------	---	--------------------------

%CD11a+ [Neut]	A4S54	CD11a+ (% of neutrophils)	VLA-4/LFA-1 Expression
%CD49d+ (9F10) [CD11c++]	A4S95	CD49d+ (% of dendritic cells [CD11c++])	VLA-4/LFA-1 Expression
%CD49d+ (9F10) [CD19+]	A4S81	CD49d+ (% of B cells)	VLA-4/LFA-1 Expression
%CD49d+ (9F10) [CD3+]	A4S67	CD49d+ (% of T cells)	VLA-4/LFA-1 Expression
%CD49d+ (9F10) [Lymphs]	A4S25	CD49d+ (% of lymphocytes)	VLA-4/LFA-1 Expression
%CD49d+ (9F10) [MNC]	A4S11	CD49d+ (% of MNC)	VLA-4/LFA-1 Expression
%CD49d+ (9F10) [Monos]	A4S39	CD49d+ (% of monocytes)	VLA-4/LFA-1 Expression
%CD49d+ (9F10) [Neut]	A4S53	CD49d+ (% of neutrophils)	VLA-4/LFA-1 Expression
MESF Total CD11a [CD11c++]	A4S92	CD11a+ dendritic cells [CD11c++] (MESF)	VLA-4/LFA-1 Expression
MESF Total CD11a [CD19+]	A4S78	CD11a+ B cells (MESF)	VLA-4/LFA-1 Expression
MESF Total CD11a [CD3+]	A4S64	CD11a+ T cells (MESF)	VLA-4/LFA-1 Expression
MESF Total CD11a [Lymphs]	A4S22	CD11a+ lymphocytes (MESF)	VLA-4/LFA-1 Expression
MESF Total CD11a [MNC]	A4S08	CD11a+ MNC (MESF)	VLA-4/LFA-1 Expression
MESF Total CD11a [Monos]	A4S36	CD11a+ monocytes (MESF)	VLA-4/LFA-1 Expression
MESF Total CD11a [Neut]	A4S50	CD11a+ neutrophils (MESF)	VLA-4/LFA-1 Expression
MESF Total CD49d (9F10) [CD3+]	A4S63	CD49d+ dendritic cells [CD11c++] (MESF)	VLA-4/LFA-1 Expression
MESF Total CD49d (9F10) [MNC]	A4S07	CD49d+ B cells (MESF)	VLA-4/LFA-1 Expression
MESF Total CD49d (9F10) [Neut]	A4S49	CD49d+ T cells (MESF)	VLA-4/LFA-1 Expression

CONFIDENTIAL

The information contained herein may not be used, disclosed, or published without the written consent of
Biogen Idec MA Inc.

biogen idec	Protocol 109MS310 An Open-Label Study to Assess the Effects of BG00012 on Lymphocyte Subsets in Subjects With RRMS	Final Version 1.0
--------------------	---	--------------------------

MESF Total CD49d [CD11c++]	A4S91	CD49d+ lymphocytes (MESF)	VLA-4/LFA-1 Expression
MESF Total CD49d [CD19+]	A4S77	CD49d+ MNC (MESF)	VLA-4/LFA-1 Expression
MESF Total CD49d [Lymphs]	A4S21	CD49d+ monocytes (MESF)	VLA-4/LFA-1 Expression
MESF Total CD49d [Monos]	A4S35	CD49d+ neutrophils (MESF)	VLA-4/LFA-1 Expression
%CD14+ [CD45+]	DMNK02	Total monocytes [CD14+] (% of CD45+ leukocytes)	Myeloid and NK cell subsets
%CD16+/CD14+dim [CD45+]	DMNK04	Non-classical Monocytes (% of CD45+ leukocytes)	Myeloid and NK cell subsets
%CD16+/CD56hi/3-/19- [Lymphs]	DMNK10	CD56 ^{Bright} NK cells (% of lymphocytes)	Myeloid and NK cell subsets
%CD16+/CD56low/3-/19- [Lymphs]	DMNK09	CD56 ^{Dim} NK cells (% of lymphocytes)	Myeloid and NK cell subsets
%CD16-/CD14+ [CD45+]	DMNK03	Classical Monocytes (% of CD45+ leukocytes)	Myeloid and NK cell subsets
%HLA-DR+ [MNC]	DMNK06	Total dendritic cells (% of MNC)	Myeloid and NK cell subsets
%HLA-DR+/CD11c+ [MNC]	DMNK07	Myeloid dendritic cells (% of MNC)	Myeloid and NK cell subsets
%HLA-DR+/CD123+ [MNC]	DMNK08	Plasmacytoid dendritic cells (% of MNC)	Myeloid and NK cell subsets
Abs CD16+/CD56hi/3-/19- Lymphs	DMNK20	CD56 ^{Bright} NK cells (cells/mm3)	Myeloid and NK cell subsets
AbsCD16+/CD56low/3-/19- Lymphs	DMNK19	CD56 ^{Dim} NK cells (cells/mm3)	Myeloid and NK cell subsets
Absolute CD14+	DMNK12	Total monocytes [CD14+] (cells/mm3)	Myeloid and NK cell subsets
Absolute CD16+/CD14+dim	DMNK14	Non-classical Monocytes (cells/mm3)	Myeloid and NK cell subsets
Absolute CD16-/CD14+	DMNK13	Classical Monocytes (cells/mm3)	Myeloid and NK cell subsets
Absolute HLA-DR+ [MNC]	DMNK16	Total dendritic cells (cells/mm3)	Myeloid and NK cell subsets

CONFIDENTIAL

The information contained herein may not be used, disclosed, or published without the written consent of Biogen Idec MA Inc.

biogen idec	Protocol 109MS310 An Open-Label Study to Assess the Effects of BG00012 on Lymphocyte Subsets in Subjects With RRMS	Final Version 1.0
--------------------	---	--------------------------

Absolute HLA-DR+/CD11c+ [MNC]	DMNK17	Myeloid dendritic cells (cells/mm3)	Myeloid and NK cell subsets
Absolute HLA-DR+/CD123+ [MNC]	DMNK18	Plasmacytoid dendritic cells (cells/mm3)	Myeloid and NK cell subsets
%45+/25+/127low/- [3+/4+]	TCTR22	Regulatory T-cells (% of CD4+ T cells)	T cell subsets
%45+/25+/127low/-/45RO-[3+/4+]	TCTR25	Naïve Regulatory T-cells (% of CD4+ T cells)	T cell subsets
%45+/25+/127low/45RO+ [3+/4+]	TCTR26	Effector Regulatory T-cells (% of CD4+ T cells)	T cell subsets
%45+25+127low45RO+DR+[3+4+]	TCTR075	Terminal Effector Regulatory T-cells (% of CD4+ T cells)	T cell subsets
%CD38+ [3+/4+/8-]	TCTR069	Activated [CD38+] (% of CD4+ T cells)	T cell subsets
%CD38+ [3+/4-/8+]	TCTR072	Activated [CD38+] (% of CD8+ T cells)	T cell subsets
%CD38+/HLA-DR+ [CD3+/CD4+]	TCTR14	Activated [CD38+HLA-DR+] (% of CD4+ T cells)	T cell subsets
%CD38+/HLA-DR+ [CD3+/CD8+]	TCTR21	Activated [CD38+HLA-DR+] (% of CD8+ T cells)	T cell subsets
%CD4+/CD45RA+ [CD3+]	TCTR08	Naïve CD4+ T-cell [CD45RA+] (% of T cells)	T cell subsets
%CD4+/CD45RA- [CD3+]	TCTR09	Memory CD4+ T-cell [CD45RA-] (% of T cells)	T cell subsets
%CD45RA+/CCR7+ [CD3+/CD4+]	TCTR10	Naïve CD4+ T-cell [CD45RA+CCR7+] (% of CD4+ T cells)	T cell subsets
%CD45RA+/CCR7+ [CD3+/CD8+]	TCTR17	Naïve CD8+ T-cell [CD45RA+CCR7+] (% of CD8+ T cells)	T cell subsets
%CD45RA+/CCR7- [CD3+/CD4+]	TCTR11	Effector CD4+ T-cell [CD45RA+CCR7-] (% of CD4+ T cells)	T cell subsets
%CD45RA+/CCR7- [CD3+/CD8+]	TCTR18	Effector CD8+ T-cell [CD45RA+CCR7-] (% of CD8+ T cells)	T cell subsets
%CD45RA-/CCR7+ [CD3+/CD4+]	TCTR12	Central Memory CD4+ T-cell [CD45RA-CCR7+] (% of CD4+ T cells)	T cell subsets
%CD45RA-/CCR7+ [CD3+/CD8+]	TCTR19	Central Memory CD8+ T-cell [CD45RA-CCR7+] (% of CD8+ T cells)	T cell subsets
%CD45RA-/CCR7- [CD3+/CD4+]	TCTR13	Effector Memory CD4+ T-cell [CD45RA-CCR7-] (% of CD4+ T cells)	T cell subsets

CONFIDENTIAL

The information contained herein may not be used, disclosed, or published without the written consent of Biogen Idec MA Inc.

biogen idec	Protocol 109MS310 An Open-Label Study to Assess the Effects of BG00012 on Lymphocyte Subsets in Subjects With RRMS	Final Version 1.0
--------------------	---	--------------------------

%CD45RA-/CCR7- [CD3+/CD8+]	TCTR20	Effector Memory CD8+ T-cell [CD45RA- CCR7-] (% of CD8+T cells)	T cell subsets
%CD8+/CD45RA+ [CD3+]	TCTR15	Naïve CD8+ T-cell [CD45RA+] (% of T cells)	T cell subsets
%CD8+/CD45RA- [CD3+]	TCTR16	Memory CD8+ T-cell [CD45RA-] (% of T cells)	T cell subsets
%CXCR3+/CCR6- [CD3+/CD4+]	TCTR29	Th1 phenotype (% of CD4+ T cells)	T cell subsets
%CXCR3+CCR6-38+HLA-DR+ [3+4+]	TCTR32	Activated Th1 phenotype (% of CD4+ T cells)	T cell subsets
%CXCR3-/CCR6+ [CD3+/CD4+]	TCTR31	Th17 phenotype (% of CD4+ T cells)	T cell subsets
%CXCR3-/CCR6- [CD3+/CD4+]	TCTR30	Th2-enriched phenotype (% of CD4+ T cells)	T cell subsets
%CXCR3-CCR6+38+HLA-DR+ [3+4+]	TCTR34	Activated Th17 phenotype (% of CD4+ T cells)	T cell subsets
%CXCR3-CCR6-38+HLA-DR+ [3+4+]	TCTR33	Activated Th2-enriched phenotype (% of CD4+ T cells)	T cell subsets
%HLA-DR+ [3+/4+/8-]	TCTR068	Activated [HLA-DR+] (% of CD4+ T cells)	T cell subsets
%HLA-DR+ [3+/4-/8+]	TCTR071	Activated [HLA-DR+] (% of CD8+ T cells)	T cell subsets
Abs 45+25+127low/-45RO-[3+4+]	TCTR56	Naïve Regulatory T-cells (cells/mm3)	T cell subsets
Abs 45+25+127low45RO+ [3+4+]	TCTR57	Effector Regulatory T-cells (cells/mm3)	T cell subsets
Abs 45+25+127low45RO+DR+[3+4+]	TCTR084	Terminal Effector Regulatory T-cells (cells/mm3)	T cell subsets
AbsCXCR3+CCR6-38+HLA-DR+[3+4+]	TCTR63	Activated Th1 phenotype (cells/mm3)	T cell subsets
AbsCXCR3-CCR6+38+HLA-DR+[3+4+]	TCTR65	Activated Th17 phenotype (cells/mm3)	T cell subsets
AbsCXCR3-CCR6-38+HLA-DR+[3+4+]	TCTR64	Activated Th2-enriched phenotype (cells/mm3)	T cell subsets
Absolute 38+/HLA-DR+ [3+/8+]	TCTR52	Activated CD8+ T-cell [CD38+HLA-DR+] (cells/mm3)	T cell subsets
Absolute 38+/HLA-DR+ [3+/4+]	TCTR45	Activated CD4+ T-cell [CD38+HLA-DR+] (cells/mm3)	T cell subsets
Absolute 45+25+127low/- [3+4+]	TCTR53	Regulatory T-cells (cells/mm3)	T cell subsets

CONFIDENTIAL

The information contained herein may not be used, disclosed, or published without the written consent of Biogen Idec MA Inc.

biogen idec	Protocol 109MS310 An Open-Label Study to Assess the Effects of BG00012 on Lymphocyte Subsets in Subjects With RRMS	Final Version 1.0
--------------------	---	--------------------------

Absolute 45RA+/CCR7+ [3+/4+]	TCTR41	Naïve CD4+ T-cell [CD45RA+CCR7+] (cells/mm3)	T cell subsets
Absolute 45RA+/CCR7+ [3+/8+]	TCTR48	Naïve CD8+ T-cell [CD45RA+CCR7+] (cells/mm3)	T cell subsets
Absolute 45RA+/CCR7- [3+/4+]	TCTR42	Effector CD4+ T-cell [CD45RA+CCR7-] (cells/mm3)	T cell subsets
Absolute 45RA+/CCR7- [3+/8+]	TCTR49	Effector CD8+ T-cell [CD45RA+CCR7-] (cells/mm3)	T cell subsets
Absolute 45RA-/CCR7+ [3+/4+]	TCTR43	Central Memory CD4+ T-cell [CD45RA-CCR7+] (cells/mm3)	T cell subsets
Absolute 45RA-/CCR7+ [3+/8+]	TCTR50	Central Memory CD8+ T-cell [CD45RA-CCR7+] (cells/mm3)	T cell subsets
Absolute 45RA-/CCR7- [3+/4+]	TCTR44	Effector Memory CD4+ T-cell [CD45RA-CCR7-] (cells/mm3)	T cell subsets
Absolute 45RA-/CCR7- [3+/8+]	TCTR51	Effector Memory CD8+ T-cell [CD45RA-CCR7-] (cells/mm3)	T cell subsets
Absolute CD38+ [3+/4+/8-]	TCTR078	Activated CD4+ T-cell [CD38+] (cells/mm3)	T cell subsets
Absolute CD38+ [3+/4-/8+]	TCTR081	Activated CD8+ T-cell [CD38+] (cells/mm3)	T cell subsets
Absolute CD4+/CD45RA+ [CD3+]	TCTR39	Naïve CD4+ T-cell [CD45RA+]	T cell subsets
Absolute CD4+/CD45RA- [CD3+]	TCTR40	Memory CD4+ T-cell [CD45RA-]	T cell subsets
Absolute CD8+/CD45RA+ [CD3+]	TCTR46	Naïve CD8+ T-cell [CD45RA+]	T cell subsets
Absolute CD8+/CD45RA- [CD3+]	TCTR47	Memory CD8+ T-cell [CD45RA-]	T cell subsets
Absolute CXCR3+/CCR6- [3+/4+]	TCTR60	Th1 phenotype (cells/mm3)	T cell subsets
Absolute CXCR3-/CCR6+ [3+/4+]	TCTR62	Th17 phenotype (cells/mm3)	T cell subsets
Absolute CXCR3-/CCR6- [3+/4+]	TCTR61	Th2-enriched phenotype (cells/mm3)	T cell subsets
Absolute HLA-DR+ [3+/4+/8-]	TCTR077	Activated CD4+ T-cell [HLA-DR+]	T cell subsets
Absolute HLA-DR+ [3+/4-/8+]	TCTR080	Activated CD8+ T-cell [HLA-DR+]	T cell subsets

CONFIDENTIAL

The information contained herein may not be used, disclosed, or published without the written consent of Biogen Idec MA Inc.

biogen idec	Protocol 109MS310 An Open-Label Study to Assess the Effects of BG00012 on Lymphocyte Subsets in Subjects With RRMS	Final Version 1.0
--------------------	---	--------------------------

%IFNg+/ IL-17A- [3+/8+] Stim	ICT56	IFNg+ (% of CD8+ T cells)	Intracellular T cell Cytokines
%IFNg+/IL-17A- [CD3+/CD4+]Stim	ICT30	IFNg+ (% of CD4+ T cells)	Intracellular T cell Cytokines
%IFNg+/IL-17A-[3+4+8-45RA-]St	ICT39	IFNg+ (% of memory CD4+ T cells)	Intracellular T cell Cytokines
%IFNg+/IL-17A-[3+8+4-45RA-]St	ICT61	IFNg+ (% of memory CD8+ T cells)	Intracellular T cell Cytokines
%IL-17A+/IFNg- [3+/8+] Stim	ICT58	IL-17A+/IFNg- (% of CD8+ T cells)	Intracellular T cell Cytokines
%IL-17A+/IFNg- [CD3+/CD4+]Stim	ICT32	IL-17A+/IFNg- (% of CD4+ T cells)	Intracellular T cell Cytokines
%IL-17A+/IFNg-[3+4+8-45RA-]St	ICT41	IL-17A+/IFNg- (% of memory CD4+ T cells)	Intracellular T cell Cytokines
%IL-17A+/IFNg-[3+8+4-45RA-]St	ICT63	IL-17A+/IFNg- (% of memory CD8+ T cells)	Intracellular T cell Cytokines
%IL-2+ [3+/4+/8-/45RA-] Stim	ICT42	IL-2+ (% of memory CD4+ T cells)	Intracellular T cell Cytokines
%IL-2+ [3+8+4-45RA-]St	ICT64	IL-2+ (% of memory CD8+ T cells)	Intracellular T cell Cytokines
%IL-2+ [CD3+/CD4+] Stim	ICT33	IL-2+ (% of CD4+ T cells)	Intracellular T cell Cytokines
%IL-2+ [CD3+/CD8+] Stim	ICT59	IL-2+ (% of CD8+ T cells)	Intracellular T cell Cytokines
%IL-4+ [3+/4+/8-/45RA-]Stim	ICT40	IL-4+ (% of memory CD4+ T cells)	Intracellular T cell Cytokines
%IL-4+ [3+8+4-45RA-] Stim	ICT62	IL-4+ (% of memory CD8+ T cells)	Intracellular T cell Cytokines
%IL-4+ [CD3+/CD4+] Stim	ICT31	IL-4+ (% of CD4+ T cells)	Intracellular T cell Cytokines
%IL-4+ [CD3+/CD8+] Stim	ICT57	IL-4+ (% of CD8+ T cells)	Intracellular T cell Cytokines
% Granulocytes	PGRANS	Granulocytes (% of leukocytes)	TBNK Lymphocyte Subsets
% Lymphocytes	PLYMPH	Lymphocytes(% of leukocytes)	TBNK Lymphocyte Subsets

CONFIDENTIAL

The information contained herein may not be used, disclosed, or published without the written consent of Biogen Idec MA Inc.

[figure not shown]
biogen idec	Protocol 109MS310 An Open-Label Study to Assess the Effects of BG00012 on Lymphocyte Subsets in Subjects With RRMS	Final Version 1.0
--------------------	---	--------------------------

% Monocytes	PMONOS	Monocytes (% of leukocytes)	TBNK Lymphocyte Subsets
%CD19+ (TBNK TruCount BD)	CD19P1	B cells (% of lymphocytes)	TBNK Lymphocyte Subsets
%CD3+ [Tube 1]	CD3P1	T cells (% of lymphocytes)	TBNK Lymphocyte Subsets
%CD3+/CD4+	CD4P1	CD4+ T cells (% of lymphocytes)	TBNK Lymphocyte Subsets
%CD3+/CD8+	CD8P1	CD8+ T cells (% of lymphocytes)	TBNK Lymphocyte Subsets
%CD3-/CD16+,CD56+	NK2P1	NK cells (% of lymphocytes)	TBNK Lymphocyte Subsets
Abs Granulocytes	AGRANS	Granulocytes (cells/mm3)	TBNK Lymphocyte Subsets
Abs Monocytes	AMONOS	Monocytes (cells/mm3)	TBNK Lymphocyte Subsets
Absolute CD3+ [Tube 1]	CD3A1	T Cells (cells/mm3)	TBNK Lymphocyte Subsets
Absolute Lymphocytes [Tube 1]	ALYMT1	Lymphocytes (cells/mm3)	TBNK Lymphocyte Subsets
CD16,56 Absolute	NK2A	NK cells (cells/mm3)	TBNK Lymphocyte Subsets
CD19 Absolute	CD19A	B cells (cells/mm3)	TBNK Lymphocyte Subsets
CD4 Absolute	CD4A	CD4+ T cells (cells/mm3)	TBNK Lymphocyte Subsets
CD8 Absolute	CD8A	CD8+ T cells (cells/mm3)	TBNK Lymphocyte Subsets

CONFIDENTIAL

[figure not shown]
The information contained herein may not be used, disclosed, or published without the written consent of Biogen Idec MA Inc.

	
Protocol 109MS310 An Open-Label Study to Assess the Effects of BG00012 on Lymphocyte Subsets in Subjects With RRMS
	Final Version 1.0
---	---	--------------------------

CONFIDENTIAL

[figure not shown]
The information contained herein may not be used, disclosed, or published without the written consent of
Biogen Idec MA Inc.

CONFIDENTIAL

The information contained herein may not be used, disclosed, or published without the written consent of
Biogen Idec MA Inc.

	
Protocol 109MS310 An Open-Label Study to Assess the Effects of BG00012 on Lymphocyte Subsets in Subjects With RRMS
	Final Version 1.0
---	---	--------------------------

CONFIDENTIAL

The information contained herein may not be used, disclosed, or published without the written consent of
Biogen Idec MA Inc.

biogen idec	Protocol 109MS310 An Open-Label Study to Assess the Effects of BG00012 on Lymphocyte Subsets in Subjects With RRMS	Final Version 1.0
--------------------	---	--------------------------

